Interventions because of the trial

Personalised alarm cut-offs can be programmed by the caregiver team. There is no scheduled study contact on top of the usual care contacts. In case of application alarms being triggered, the patient will be called and the situation will be assessed. If needed, the problem will be discussed with a cardiologist. In emergency situations, the patient will be asked to present to the emergency department.

Monitoring of alarms will not be continuous and will only take place during working hours throughout the working week (Monday to Friday) and patients will be instructed to call their general practitioner, the hospital, or the emergency number in case of problems and not to wait until they are contacted.

End-of-trial assessment

At the end of the trial, the assessments listed in Table 2 will be performed. Cost-related data will be collected: healthcare resource use, hospitalisation time, tests, procedures, and health expenditure. Cost-effectiveness will be calculated using healthcare cost data and work productivity and impairment (WPAI) questionnaire to calculate incremental cost-effectiveness ratio (ICER).

Re-evaluation at 12 months

After the end of the inclusion at 6 months, a re-evaluation of outcome parameters will take place at month 12 to evaluate the continued effect of the intervention after cessation.

	Baseline	Final visit month 6
Informed consent and patient information	X	
Medical history: past medical history, symptom control, NYHA classification, smoking behaviour, current medication	X	X
Physical examination including weight, height, blood pressure, heart rate	X	X
Length of initial hospital stay	X	
Registration of medication	X	X
Echocardiography	X	X
12-lead ECG	X	X
Laboratory tests: haemoglobin, haematocrit, leukocytes, thrombocytes, sodium, potassium, creatinine, NT-proBNP	X	X
ePROs: KCCQ-12, EQ5D, HeartQoL, PHQ9, HLS-EU-Q16, EHFSB-9, SUTAQ, WPAI.	X	X
Registration of events: hospitalisation (with the length of stay), emergency department visit, death		X
Cost-evaluation		X

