Cost reduction between the intervention group, the historical cohort, and the participation refusals will be calculated. Costs and outcomes (utilities) will be compared by calculation of the incremental cost-effectiveness ratio (ICER) (ICER = $(\text{cost}_{\text{intervention group}} - \text{cost}_{\text{historical cohort}}) / (\text{effectiveness}_{\text{intervention group}} - \text{effectiveness}_{\text{historical cohort}})$). The incremental cost represents the difference in total average cost per patient between the intervention group and the historical cohort or the participation refusals. Effectiveness will be calculated by comparing QOL in the intervention group versus the participation refusals.

Study endpoints

The endpoints that will be assessed are summarized in Table 3. As specified before, the objectives of the study are to demonstrate positive implementation measures (e.g. feasibility) as well as to demonstrate cost-effectiveness. Secondary objectives include assessment of clinical impact, based on measurement of clinical endpoints as specified in Table 3. Implementation outcome variables will be assessed using a mixed-method design. Patient and caregiver parameters will be calculated (e.g. time spent using the application). Questionnaires will be used to assess patient variables. Semi-structured interviews in a selection of patients and caregivers will be performed to assess further outcome variables regarding implementation.

Implementation outcome variables	
Feasibility and patient acceptability	SUTAQ, semi-structured interviews.
Caregiver acceptability and burden of care	SUTAQ, semi-structured interviews, daily time spent by case nurses using the platform
Adoption and sustainability	Number and percentage of patients refusing inclusion, of patients continuing application usage after 6 months. Total time-percentage ratio of patients using the application throughout the trial.
Implementation cost	Cost-related data: healthcare resource use, hospital days, tests, procedures, health expenditure. Cost-effectiveness: healthcare cost data, WPAI questionnaire, ICER. Cost of hospital stay at inclusion.
Quality of life, literacy and patient self-care	KCCQ-12, EQ5D, HeartQoL, PHQ9, HLS-EU-Q16, EHFSB-9, SUTAQ.
Clinical outcome measurement	
Combined endpoint	Unplanned CV readmission and all-cause mortality

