Individual endpoints	Symptom control (NYHA, KCCQ-12), emergency department visits, length of hospital stay during the trial, unplanned CV readmission, all-cause mortality.

Table 3 - Study endpoints. CV: cardiovascular. SUTAQ: Service User Technology Acceptability Questionnaire. KCCQ-12: Kansas City Cardiomyopathy Questionnaire. EQ5D: EuroQol 5-dimension questionnaire. HeartQoL: Health-related quality of life questionnaire. PHQ9: patient health questionnaire-9. HLS-EU-Q16: European Health Literacy Survey Questionnaire. EHFSB-9: European Heart Failure Self-care Behaviour scale revised into a nine-item scale. SUTAQ: Service User Technology Acceptability Questionnaire. WPAI : work productivity and impairment. ICER: incremental cost-effectiveness ratio.

Statistical analysis

Sample size

A total of 165 patients will be included in the study. The sample size is based on comparable implementation trials (9,10). An additional patient group will be included that is not part of the study intervention but will complete questionnaires; this is a non-randomized control group. A minimum of 165 patients will take part in this control group for completion of the study.

Statistical analysis

The primary analyses will be paired Student *t*-tests and Wilcoxon signed-rank tests comparing baseline, 6-month and 12-month values for all patient-level outcomes. Secondary analyses aimed at determining the longitudinal impact of the smartphone digital support programme (i.e., using outcome data from the additional time points), and the correlation of independent variables (e.g., patient characteristics and adherence rates) with outcomes will be analysed using general linear mixed-model procedures. In addition, descriptive statistics will be produced for all variables collected, and subgroup analyses will be performed. All statistical analyses will be performed using the statistical software application SPSS (IBM Corporation, USA).

Descriptive statistics will be produced for the indicators of the implementation outcome to provide an objective measure of implementation success.

Discussion

The Bedicare-HF study is the first study that will investigate implementation of a smartphone-based HF digital support system in a real-life context on the background of European GDPR and medical device regulations.

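### The only regression named for relating patient factors to outcomes is a general linear mixed model, which does not suit the event, count, hospital-day and NYHA endpoints; its intervals can be too narrow or too wide

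*Protocol*

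**What the plan says.** The protocol's Statistical analysis section has two tiers. The primary tier is paired t-tests and Wilcoxon signed-rank tests, "comparing baseline, 6-month and 12-month values for all patient-level outcomes". The secondary tier covers longitudinal impact and "the correlation of independent variables (e.g., patient characteristics and adherence rates) with outcomes". Both parts of the secondary tier "will be analysed using general linear mixed-model procedures". No distribution, link function or other regression is named.

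Table 3 mixes outcome types. Under implementation outcomes it lists questionnaires: "KCCQ-12, EQ5D, HeartQoL, PHQ9, HLS-EU-Q16, EHFSB-9, SUTAQ". Under clinical outcomes it gives a combined endpoint, "Unplanned CV readmission and all-cause mortality", and individual endpoints: "Symptom control (NYHA, KCCQ-12), emergency department visits, length of hospital stay during the trial, unplanned CV readmission, all-cause mortality". Table 2 marks the row "Registration of events: hospitalisation (with the length of stay), emergency department visit, death" at month 6 only.

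**The concern.** A general linear mixed model treats the outcome as continuous, with normal residuals of one common variance. Death, readmission and their composite are yes/no or time-to-event. Emergency visits are counts. Hospital days are a skewed duration, likely with many zeros. NYHA is an ordered class without equal spacing. For events, counts and days the variance changes with the mean, so one pooled residual variance misstates the precision of each group when the groups differ.

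At stake are the analyses meant to show which patients do well or badly. Clinical impact is a stated secondary objective in the Study endpoints section. If a small subgroup, such as poor adherers, has more events, the interval around its excess risk will look more precise than it is. If the higher-risk group is the large one, the interval will be needlessly wide. A straight-line model for a risk can also return values below zero.

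This is separate from any question about paired tests on events that have no baseline value. A regression on patient characteristics needs no baseline event count, but it does need a suitable distribution.

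**Working it through.** The protocol gives no event rates, variances, alpha or power, and no figure on this point, so there is nothing to reproduce. The check asks how a nominal 95% interval from the linear model behaves.

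**Input from the protocol.** N = 165.

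**Assumed inputs.** One two-level characteristic; one record per patient, because Table 2 records events at month 6 only; no hospital effect. Event risks 10% v 30% and 5% v 20%; mean emergency visits 0.5 v 1.0; mean hospital days 6 v 15. Counts and days are negative binomial with dispersion 1.5.

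**Formulas.** With n0 and n1 patients and variances v0 and v1:
- Pooled variance: vp = [(n0 − 1)v0 + (n1 − 1)v1] / (N − 2)
- Standard error the model reports: √[vp(1/n0 + 1/n1)]
- Actual standard error: √(v0/n0 + v1/n1)
- v = p(1 − p) for a binary outcome; v = m + 1.5m² for a count or days

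**Worked case: risk 10% v 30%, 16 patients in the higher-risk group.**
- v0 = 0.09, v1 = 0.21, n0 = 149, n1 = 16
- vp = (148 × 0.09 + 15 × 0.21)/163 = 0.101
- Model SE = √[0.101 × (1/149 + 1/16)] = 0.084
- Actual SE = √(0.09/149 + 0.21/16) = 0.117
- Ratio = 0.71, so the interval has about 71% of the width it needs.

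**Results.** Ratio of model to actual SE, then simulated coverage (40,000 data sets per cell), by size of the higher-risk group:

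| Outcome (lower v higher group) | 16 of 165 | 82 of 165 | 140 of 165 |
|---|---|---|---|
| Event risk 10% v 30% | 0.71; 82% | 1.00; 95% | 1.33; 99% or more |
| Event risk 5% v 20% | 0.62; 75% | 1.00; 95% | 1.49; 99% or more |
| Emergency visits 0.5 v 1.0 | 0.66; 81% | 1.00; 94-95% | 1.42; 99% or more |
| Hospital days 6 v 15 | 0.52; 68% | 1.00; 94% | 1.72; 99% or more |

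**Milder imbalance (80:20), same event risks.** Coverage is 87% and 83% when the small group has the higher risk, and about 99% when it has the lower.

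**No true association.** Equal risks or means give equal variances, so the ratio is 1. Simulated false-positive rates were 3.5-5.2% for binary outcomes and 4.4-5.1% for counts and days, against a nominal 5%.

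**NYHA.** A paired mean change in NYHA was covered at 95.3%. The case against the linear model for NYHA is therefore the ordinal scale, not a demonstrated loss of coverage.

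**Negative risks.** With logit(p) = −2.5 + z, z standard normal (average risk about 10.6%), about 11% of fitted linear risks fell below zero.

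**Alternatives.** In the unbalanced scenarios of the table, plain logistic and negative binomial fits covered about 93% to 97.5%. Keeping the linear model with unequal variances gave about 92-94% for binary outcomes at 80:20. It gave only 86-95% for a more skewed hospital-day distribution (means 3 and 6), so a variance correction alone does not fully cure that outcome.

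**The case against.** Several counter-arguments have weight.

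- **Scope.** A reader might infer that the protocol imposes this model on every outcome. It does not say so: the word 'all' stands in the sentence on the primary tests. The secondary sentence says only 'outcomes', and it opens with longitudinal impact, where mixed models for repeated questionnaire scores are natural. This narrows the point but does not remove it, because nothing excludes the clinical endpoints and no other regression is offered for them.
- **False associations.** A reader might infer that narrow intervals produce spurious findings. In the setting checked they do not. With no true difference the variances are equal and the error rate is nominal. What is shown is misstated precision around a real difference.
- **Conditional error.** The intervals are not always wrong. The failure needs both an unbalanced characteristic and a true association. All rates are assumed.
- **Simplified simulation.** With one record per patient and no hospital effect, the model reduces to a pooled two-group comparison. A full mixed model with repeated scores was not tested, nor were mixed versions of the alternatives.
- **Detail for the SAP.** Link functions are often left to the SAP, and the wording may be a loose form of generalised linear mixed model. But the protocol does not leave the method open: it names one. A SAP using logistic or negative binomial models would depart from that sentence, and if generalised models were meant, the same edit is needed.

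**Conclusion.** The point holds in a limited form. The one regression named is unsuitable for the binary, count, skewed-duration and ordinal clinical endpoints of Table 3, and suitable for the questionnaire scores. Under the assumed rates, coverage of a nominal 95% interval ranges from about 68% to above 99% when a characteristic is unbalanced and truly related to the outcome. It stays at about 94-95% when the groups are balanced. The evidence supports saying that intervals can be wrong in either direction, not that they will be. It does not support a claim of inflated false-positive rates. The direction and size of the error depend on event rates and subgroup sizes that the protocol does not give. The consequence is confined to secondary analyses; the primary paired tests are untouched by this point.

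**What to change.** In the Statistical analysis section, replace the single model with one named by outcome type:

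- Questionnaire scores: linear mixed models, as now.
- Readmission, death and their composite: logistic regression, or Cox regression where event dates exist. The planned 30-day and 90-day rehospitalisation rates imply that the timing of readmissions will be known.
- Emergency visits and hospital days: negative binomial regression with the log of follow-up time as offset.
- NYHA class: an ordinal (cumulative logit) model.
- Hospital: a random effect only where event numbers support it. With 11 hospitals and few deaths, such a model may fail to converge.

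The cost is a sentence or two of text, with no extra patients or data. SPSS, the software already named, fits these models. There are two downsides. Effects will be reported as odds, rate or hazard ratios instead of mean differences. Sparse events such as death may support only very simple models with few covariates.

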[figure not shown]

Figure 1 – The Comunicare patient platform. The parameter module is displayed.
